4.6.2 Secondary Efficacy Analysis

All secondary endpoints will be analysed on the FAS and the PPS. All statistical tests will be performed at a 5% level (2-sided).

Percentage of subjects achieving an increase in Hb $\geq 2\text{ g/dL}$ from baseline at Weeks 2, 4, 6 and 8. The difference in proportions between the FCM and Venofer groups from baseline at Weeks 2, 4, 6 and 8 and its two-sided 95% confidence intervals (CIs) will be computed using the Wilson score method with continuity correction described by Newcombe (1998).

Change in Hb from baseline to Weeks 2, 4, 6 and 8. Summary statistics will be presented at baseline, Weeks 2, 4, 6 and 8. Treatment comparisons for change in Hb from baseline will also be assessed using an analysis of MMRM model including treatment, haemoglobin baseline, site and visit as factors. Interaction between visit and treatment is also included in the model. The covariance structure to model the within-subject errors will be unstructured. The REML will be used. The Kenward-Roger method will be used to estimate the denominator degrees of freedom. Type III tests for the least-squares (LS) means will be used for the statistical comparison; the 95% CI will also be reported. Treatment group comparisons at each visits will be reported. If the unstructured covariance matrix results in a lack of convergence, the heterogeneous Toeplitz covariance structure, followed by the heterogeneous autoregressive covariance structure, followed by the compound symmetry will be used. This order is specified according to a decreasing number of covariance parameters in the structure.

The percentage of subjects with ID correction defined as TSAT $\geq 16\%$ and serum ferritin $\geq 100\text{ ng/mL}$ (for subjects with underlying inflammatory disease as determined by hsCRP levels above the normal range) or $> 14\text{ng/mL}$ (in subjects with no apparent underlying inflammatory disease as determined by hsCRP levels within normal range) at Weeks 2, 4, 6 and 8. The difference in proportions between the FCM and Venofer groups at Weeks 2, 4, 6 and 8 and its two-sided 95% confidence intervals (CIs) will be computed using the Wilson score method with continuity correction described by Newcombe

(1998). Treatment comparisons of subjects with ID correction variable will be assessed using a logistic regression analysis with treatment, baseline serum ferritin, baseline TSAT, and site in the model.

Change in TSAT from baseline to Weeks 2, 4, 6 and 8. Summary statistics will be presented at baseline, Weeks 2, 4, 6 and 8. Treatment comparisons for Change in TSAT from baseline will also be assessed using an analysis of MMRM model including treatment, haemoglobin baseline, site and visit as factors. Interaction between visit and treatment is also included in the model. The covariance structure to model the within-subject errors will be unstructured. The REML will be used. The Kenward-Roger method will be used to estimate the denominator degrees of freedom. Type III tests for the least-squares (LS) means will be used for the statistical comparison; the 95% CI will also be reported. Treatment group comparisons at each visits will be reported. If the unstructured covariance matrix results in a lack of convergence, the heterogeneous Toeplitz covariance structure, followed by the heterogeneous autoregressive covariance structure, followed by the compound symmetry will be used. This order is specified according to a decreasing number of covariance parameters in the structure.

Change in serum ferritin from baseline to Weeks 2, 4, 6 and 8. Summary statistics will be presented at baseline, Weeks 2, 4, 6 and 8. Treatment comparisons for Change in serum ferritin from baseline will also be assessed using an analysis of MMRM model including treatment, haemoglobin baseline, site and visit as factors. Interaction between visit and treatment is also included in the model. The covariance structure to model the within-subject errors will be unstructured. The REML will be used. The Kenward-Roger method will be used to estimate the denominator degrees of freedom. Type III tests for the least-squares (LS) means will be used for the statistical comparison; the 95% CI will also be reported. Treatment group comparisons at each visits will be reported. If the unstructured covariance matrix results in a lack of convergence, the heterogeneous Toeplitz covariance structure, followed by the heterogeneous autoregressive covariance structure, followed by the compound symmetry will be used. This order is specified according to a decreasing number of covariance parameters in the structure.

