2.2 Dose and Drug Selection

Ferric carboxymaltose is an IV iron preparation which, in Europe, is indicated for subjects with ID when oral iron preparations are ineffective or cannot be used. It is a Type 1 iron complex with a low risk of toxicity as Type 1 iron complexes are stable and robust complexes [13]. As such, FCM provides iron for the endogenous iron transport and storage proteins in a controlled manner. This permits FCM to be administered in individual dosing at up to 1,000 mg iron at relatively short time intervals. Moreover, being free of dextran or dextran derivatives, FCM has no risk of dextran-induced immunogenicity. Nevertheless, as with all IV iron preparations, FCM may induce hypersensitivity reactions (see Section 8.1).

The IB summarises data from over 30 completed clinical trials with FCM which supports the administration of doses of up to 1,000 mg per administration, with an approved maximum single dose of 20 mg iron/kg BW.

Traditionally the Ganzoni formula has been used to calculate total iron requirements [9]. However, Evstatiev et al, 2011 [15] have recently demonstrated that FCM dosed using a simplified dosing formula (as proposed in this study) is superior in efficacy to dosing using the Ganzoni formula (using Venofer at multiple 200 mg iron doses). The simplified dosing formula (Table 2) is calculated based on subject BW and Hb. Using this standard formula, the heaviest subjects with low Hb receive the highest cumulative iron doses.

As such, FCM will be administered using this simplified formula for calculating the total iron dose to achieve appropriate repletion of iron requirements.

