7.2.2 Arm B: Iron Sucrose

For subjects in the individually calculated IS dosage regimen group, the individual iron deficit will be calculated using the formula of Ganzoni [9]:

Cumulative iron deficit [mg] =

$$BW [kg] \times (\text{target Hb}^{(1)} - \text{actual Hb}) [g/dL]^{(2)} \times 2.4^{(3)} + 500 \text{ mg}^{(4)}$$

⁽¹⁾ Target Hb for BW >35 kg = 15 g/dL, respectively 9.3 mmol/L

⁽²⁾ To convert mmol/L to g/dL: multiply Hb (mmol/L) by the factor 1.61145

⁽³⁾ Factor 2.4 = 0.0034 (iron content Hb = 0.34%) x 0.07 (blood volume = 7% of BW) x 10,000 (conversion g/dL to mg/L)

⁽⁴⁾ Iron storage depot

Note: BW = Body weight.

The calculated cumulative IS dose is to be rounded up or down to the nearest 200 mg.

Subjects will receive single doses of IS of up to a maximum single dose of 200mg iron three times a week. Depending on the calculated iron deficit, up to 11 IS injections will be given.

Iron Sucrose (Venofer) will be administered by slow IV push injection at a rate of 1 ml undiluted solution per minute (10 ml of the product in at least 10 minutes; administration time should not exceed 60 minutes) or by drip infusion in a dilution of 1 ml of Venofer in maximum 20 ml 0.9% w/v physiological saline (10 ml of the product in maximum 200 ml saline). Venofer must be used immediately after dilution. The drip infusion rate should be 200 ml solution in at least 30 minutes, and should not exceed 60 minutes.

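### The Hb-change MMRM fits one baseline-Hb slope to all four visits; if the true slope changes over visits, some visit contrasts lose precision

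*SAP*

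**What the plan says.** SAP 4.6.2 (Secondary Efficacy Analysis) specifies for change in Hb an "MMRM model including treatment, haemoglobin baseline, site and visit as factors. Interaction between visit and treatment is also included in the model". No other interaction is named. On covariance it says "The covariance structure to model the within-subject errors will be unstructured", with simpler structures as fallbacks, and it uses REML with Kenward-Roger degrees of freedom. On output it says "Treatment group comparisons at each visits will be reported". Tests are two-sided at 5%.

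Protocol 11.7.2 allows baseline characteristics as model terms where appropriate. It names no interaction and makes no multiplicity adjustment for secondary outcomes. Neither document contains a baseline-by-visit term. The SAP lists baseline Hb among the factors, although it is a continuous measurement.

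**The concern.** With baseline Hb as a main effect only, the model assumes that a subject starting 1 g/dL lower gains the same extra Hb at Week 2 as at Week 8. That is a strong assumption for a response that develops over the study. If it fails, the fitted slope is a compromise. At visits where the compromise is far from the true slope, the adjustment removes less of the outcome variance than it could, and the treatment difference still moves with any chance imbalance in baseline Hb. At stake are the width of the visit-specific intervals and how well they are protected against imbalance.

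**Working it through.** **The plan's own figure.** The only sizing is for the primary endpoint (Protocol 11.2, SAP 2.4): n = (1.960 + 0.842)² × 2 × 0.70 × 0.30 / 0.15² = 146.5, so 147 per group. Then 147 / 0.80 = 183.75, so 184 per group and 368 in total. This reproduces. No SD, slope or power is given for the Hb-change model.

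**Is a changing slope plausible?**
- FCM (Protocol Table 2): the Day 1 dose is the same in both Hb columns. The part that depends on Hb comes on Day 8, or on Day 15 for subjects under 50 kg.
- IS (Protocol 7.2.2): each visit gives up to 200 mg, and Hb and weight determine when dosing stops. A 60 kg subject at Hb 10 needs 60 × 5 × 2.4 + 500 = 1,220 mg, rounded to 1,200. At Hb 7 the need is 60 × 8 × 2.4 + 500 = 1,652 mg, rounded to 1,600. The table in SAP 4.5 allows 1,000 or 1,200 mg by Day 14. Both subjects can therefore have had the same iron at Week 2 and differ only later.

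**Formula (complete data).** Let β hold the true baseline slopes at the four visits, S the residual covariance, SDx the baseline SD and sd_t the residual SD at visit t. The common slope tends to b = 1'S⁻¹β / 1'S⁻¹1. Relative to a model with baseline by visit, the variance of the treatment contrast at visit t is multiplied by 1 + (β_t − b)² × SDx² / sd_t². The contrast keeps a dependence of β_t − b per g/dL of baseline imbalance.

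**Assumed inputs (none is in the documents).**
- SDx: 1.0 to 1.4 g/dL.
- Residual SD at Weeks 2/4/6/8: rising 0.8/1.0/1.2/1.3, flat 1.2, or falling 1.3/1.2/1.0/0.8.
- Within-subject correlation: 0.6 compound symmetry or 0.8 autoregressive.
- Slopes: mild −0.4/−0.5/−0.6/−0.6; moderate −0.3/−0.5/−0.65/−0.7; strong −0.2/−0.5/−0.75/−0.85.

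**Worked case.** Strong steepening, rising residual SD, autoregressive correlation, SDx 1.4: b = −0.236. The Week 8 ratio is 1 + (−0.85 + 0.236)² × 1.4² / 1.3² = 1.44.

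**Variance ratio, range over SDx and correlation:**

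| Slopes | Residual SD | Week 2 | Week 8 |
|---|---|---|---|
| Equal | any | 1.00 | 1.00 |
| Mild | rising | 1.00 | 1.02–1.04 |
| Mild | flat | 1.01–1.02 | 1.00–1.01 |
| Mild | falling | 1.02–1.05 | 1.00 |
| Moderate | rising | 1.00 | 1.08–1.17 |
| Moderate | flat | 1.03–1.08 | 1.02–1.05 |
| Moderate | falling | 1.08–1.20 | 1.00 |
| Strong | rising | 1.00–1.01 | 1.22–1.44 |
| Strong | flat | 1.08–1.19 | 1.05–1.13 |
| Strong | falling | 1.21–1.51 | 1.00–1.01 |

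**With dropout.** Simulation with 368 subjects, 20% monotone dropout, SDx 1.4, autoregressive 0.8 and 200 trials per scenario. Slopes are given as the percentage of the Hb deficit recovered at each visit. The Week 8 empirical variance ratio for rising, flat and falling residual SD was:
- 35/65/82/90% recovered: 1.42, 1.27 and 1.18
- 25/45/55/60% recovered: 1.18, 1.05 and 0.98

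In the 1.42 case the model SE was 0.133 against 0.110 g/dL, so the 95% half-width grows by 1.96 × 0.023 = 0.045 g/dL.

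**Chance imbalance.** The upper 95% limit for the baseline difference is 1.96 × 1.4 × √(2/184) = 0.29 g/dL. With rising residual SD and autoregressive correlation, the Week 8 dependence is −0.38 (moderate) or −0.61 (strong), so the shift is about 0.11 or 0.18 g/dL in size. With equal slopes it is zero.

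**Validity.** In complete-data simulations at 147 per arm (1,000 trials per scenario), bias was at most 0.007 g/dL in absolute value. Type I error of the common-slope model was 3.4% to 5.6%.

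**The case against.** The strongest reply is that the documents do not show that the slope changes, or in which direction. This stands. Protocol 2.2 says that "the heaviest subjects with low Hb receive the highest cumulative iron doses", and the Ganzoni formula uses "Target Hb for BW >35 kg = 15 g/dL". The first concerns total dose. The second is an input to the IS dose calculation, not a predicted Hb. From 50 kg upwards, the Hb-dependent FCM iron is a single step at 10 g/dL, given on Day 8, before the Week 2 visit. The dosing rules make steepening plausible and no more.

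A reader might infer that Weeks 6 and 8 in particular are under-adjusted. That also needs a fitted slope pulled towards Week 2, which happens when residual SD rises over time. If subjects converge on a normal range, residual SD could fall instead, and the loss moves to Week 2. If slopes flatten over time, the later visits can be over-adjusted.

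A reader might also take a near-complete recovery pattern (90% of the deficit by Week 8) as typical; one simulation of it gave Week 8 ratios of 1.45 (model-based) to 1.65 (empirical). It fits poorly with the planned 70% IS responder rate at any time up to Week 8. Under assumed baseline distributions within the entry limits, it implies 77% to 91% responders at Week 8 alone if recovery is towards 13 g/dL, and 97% or more towards 15 g/dL. The 60% pattern gives 54% to 86% for recovery towards 13 to 14 g/dL.

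Finally, nothing confirmatory rests on this model. The primary test is a Newcombe interval on responder proportions, and Protocol 11.7.2 warns against over-reading single secondary results. That limits the importance of the point. It does not remove the case for a better model at almost no cost.

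**Conclusion.** The point holds conditionally. The single slope follows directly from the model as written. Its cost is nil if slopes are equal. Under the assumptions above, the Week 8 variance ratio is about 1.0 to 1.2 with moderate steepening and up to about 1.4 with strong steepening and rising residual SD. With flat residual SD much of the loss is at Week 2, and with falling residual SD most of it is. The documents cannot settle which case applies.

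It should not be read as systematic bias or an inflated type I error: randomisation keeps the contrasts unbiased on average, and the complete-data simulations show the error rate held. Dropout was simulated only for precision and for dependence on imbalance. The listing of baseline Hb among the factors is loose wording to tidy, not a sign that it would be fitted as categories.

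**What to change.** In SAP 4.6.2, give the fixed effects of the Hb-change MMRM as treatment, visit, treatment by visit, baseline Hb (continuous), baseline Hb by visit, and site. Estimate the treatment difference at each visit from that model. Make the change before database lock, so that the model is not chosen after results are seen in an open-label trial.

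The cost is one sentence and 3 extra parameters, with no new data. Precision was not appreciably worse with the interaction in any simulated scenario. Protocol 11.7.2 already allows baseline terms, and Protocol 11.1 leaves detailed methods to an SAP finalised before lock, so a protocol amendment does not appear necessary.

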2. RATIONALE

Ferric carboxymaltose has been developed by Vifor Pharma – Vifor International Inc. as a formulation enabling the application of high iron doses of up to 20 mg/kg body weight as infusion, and as undiluted injection of up to 15 mg/kg body weight. Ferric carboxymaltose has a low immunogenic potential and does not exhibit cross-reactivity to anti-dextran antibodies. The application of high doses of IV iron in 1 single administration with the potential to replenish the iron stores has multiple advantages over multiple smaller doses. Compared to other IV iron products, FCM can be given in a short time (6 minutes instead of 3.5 hours for a 500 mg iron dose) and in iron doses of up to 1,000 mg, which reduced the need for the subject for multiple and long stays at the hospital. This reduces hospital costs [5]. Also, especially in rural regions, a single administration for replenishing the iron stores may help to increase subject compliance, and might make long journeys to the hospital unnecessary. A single administration versus multiple infusions additionally reduces the risks associated with the administration procedure, such as phlebitis, infection, extravasation, of other infusion-related AEs [5].

It has been seen that interethnic variability in PKs of certain drugs can cause unexpected outcomes, such as therapeutic failure, adverse effects, and toxicity in subjects of different ethnic origin, which can be both due to genetic and environmental factors. The International Conference on Harmonisation (ICH) published a guidance to facilitate the registration of drugs among ICH regions (European Union, Japan, the United States), recommending a framework for evaluating the impact of ethnic factors on efficacy and safety of drugs at a particular dosage and dosage regimen. Especially drugs metabolised via the Phase 1 enzymes of the cytochrome group are prone to ethnical and/or genetic variability [14]. Ferric carboxymaltose is not metabolised via cytochrome and constitutes a delivery system for the trace element iron. Based on limited data from Asian subjects who participated in the global registration studies conducted in Europe, genetic or interracial differences are not expected.

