9.1.3 Laboratory Parameters

All blood samples (total blood volume approximately 46ml) will be analysed at a central laboratory, Teddy Clinical Research laboratory,
[name]
[name]
[name]
[name]
China.

Blood for clinical chemistry and haematology does not have to be drawn under fasting conditions.

Haematology parameters to be analysed are Hb, haematocrit, red blood cell count, MCV, MCH, MCHC, reticulocyte count, Hb content of reticulocytes, white blood cell count with differential (absolute and percentage) and platelet count.

Iron status parameters include serum iron, serum ferritin, serum transferrin, UIBC and TSAT.

Clinical chemistry parameters to be analysed are electrolyte status (sodium, potassium, magnesium, calcium, chloride, phosphorus), glucose, AST, ALT, GGT, AP, lactate dehydrogenase and hsCRP.

Blood for safety laboratory assessments will be collected at screening, baseline, Weeks 2, 4, 6 and 8. Blood samples must always be collected prior to study drug administration.

A serum pregnancy test (for women of childbearing potential only) will be performed at screening and End of Study visit.

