11.7.2 Secondary

The secondary efficacy endpoints for this study are as follows:

- Percentage of subjects achieving an increase in Hb ≥ 2 g/dL from baseline at Weeks 2, 4, 6 and 8.
- Change in Hb from baseline to Weeks 2, 4, 6 and 8.
- The percentage of subjects with TSAT $\geq 16\%$ and serum ferritin ≥ 100 ng/mL (for subjects with underlying inflammatory disease as determined by hsCRP levels above the normal range) or serum ferritin >14 ng/mL (in subjects with no apparent underlying inflammatory disease as determined by hsCRP levels within normal range at screening) at Weeks 2, 4, 6 and 8.
- Change in TSAT from baseline to Weeks 2, 4, 6 and 8.
- Change in serum ferritin from baseline to Weeks 2, 4, 6 and 8.

Appropriate summary descriptive statistics will be determined for all secondary endpoints at each visit for the FAS population using raw scores. Where appropriate,

methods for imputing missing values for both primary and secondary analyses will be described in the SAP. If any spurious data have been identified during the data review process they will be flagged and considered as missing in the analyses. All spurious and unused data will be included and identified in individual data listings. Missing data will be shown as missing in the listings. For continuous secondary endpoints, either analysis of variance or analysis of covariance models will be used and where necessary, the repeated measures procedure will be implemented. Where appropriate, terms for treatment, gender, age and respective baseline characteristics will be included. For non-continuous endpoints, more non-parametric methods will be used to make treatment comparisons, details of which will be fully specified in the SAP. Significance level is set at an alpha of 0.05 and no adjustment will be made for testing multiple secondary outcomes. Some significant findings are expected to occur by chance so undue consideration will not be given to any particular significant difference. Moreover, interpretation of the results will be based on patterns of differences and in conjunction with the results of the primary analyses.

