2.3 Schedule of Events

Procedures	Visit			
	Visit 1 Screen	Visit 2 Baseline	Visit 3-5	Visit 6 End of study/ Early Termination
	Day -7 to Day -1	Day 1	Weeks 2, 4, 6 ±3 Days	Week 8 ±4 Days
Informed consent	✓			
Eligibility criteria	✓	✓ ⁽¹⁾		
Demographics	✓			
Medical history	✓			
Physical examination and weight	✓			✓
Height	✓			
Vital signs (blood pressure, heart rate, temperature)	✓	✓	✓	✓
Electrocardiogram	✓		✓ ⁽⁶⁾	✓
Laboratory assessments	✓	✓	✓	✓

Procedures	Visit			
	Visit 1 Screen	Visit 2 Baseline	Visit 3-5	Visit 6 End of study/ Early Termination
	Day -7 to Day -1	Day 1	Weeks 2, 4, 6 ±3 Days	Week 8 ±4 Days
(haematology/ biochemistry/iron parameters) ⁽²⁾				
Hepatitis B and C screening ⁽³⁾	✓			
Urinalysis ⁽⁴⁾	✓		✓	✓
Serum pregnancy test ⁽⁵⁾	✓			✓
Adverse events	✓	✓	✓	✓
Prior & Concomitant medications	✓	✓	✓	✓
Randomisation		✓		
Administration of study drug		✓	(✓ ⁽⁷⁾)	

1. Laboratory parameters will be tested at Baseline but will not be used for eligibility because the results will not be available on time. Laboratory parameters taken at screening will be checked for eligibility at Baseline.

2. Laboratory assessments include:

- Haematology: Hb, haematocrit, red blood cell count, MCV, MCH, MCHC, reticulocyte count, Hb content in reticulocytes, white blood cell count with differential and platelet count.
- Iron status parameters: serum iron, serum ferritin, serum transferrin, UIBC and TSAT.
- Biochemistry parameters: electrolyte status (sodium, potassium, magnesium, calcium, chloride, phosphorus), AST, ALT, gamma-glutamyl transpeptidase (GGT), glucose, alkaline phosphatase (AP), lactate dehydrogenase (LDH), C-reactive protein (CRP).

3. Hepatitis screening consists of Hepatitis B antigen, Hepatitis B virus DNA and Hepatitis C virus antibody

4. Urinalysis includes: phosphorus, protein, glucose, bilirubin, pH, nitrite, ketone, urobilinogen, blood, leukocytes

5. For women of childbearing potential only.

6. ECG is only performed at Week 4.

7. Subjects randomised to receive FCM will receive a maximum of 1,000 mg at Baseline (Day 1), a second administration of a maximum of 1,000 mg at Day 8 and a third administration of a maximum of 500 mg at Day 15, if applicable. Subjects randomised to Venofer will need to come to the study centre to receive further Venofer dosing three times a week. All study procedures must be conducted prior to dosing.

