4.1.2 Definition of baseline, visits and visit windows

The baseline will be defined as the last available (non-missing) value before or on the day of the first administration of study drug. Study day 1 is defined as the day of the first study drug administration. For analysis relative day, if considered date less than first study drug administration date, then analysis relative day will be considered date minus first study drug administration date, otherwise, it will be considered date minus first study drug administration date + 1.

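### The SAP leaves out the protocol's screening time point for the hsCRP that sets the ferritin bar for iron-deficiency correction, so the bar could be set from screening, Day 1 or visit hsCRP

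*SAP*

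**What the plan says.** Protocol 11.7.2 and the synopsis define the endpoint at Weeks 2, 4, 6 and 8 as TSAT of at least 16% together with a ferritin bar that depends on hsCRP.

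- **Normal-hsCRP branch (ferritin above 14 ng/mL).** The protocol dates the hsCRP: "as determined by hsCRP levels within normal range at screening) at Weeks 2, 4, 6 and 8".
- **Raised-hsCRP branch (ferritin at least 100 ng/mL).** The protocol gives no date: "for subjects with underlying inflammatory disease as determined by hsCRP levels above the normal range".

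SAP 2.6.2 and SAP 4.6.2 both restate the endpoint. In each, the normal branch reads "as determined by hsCRP levels within normal range) at Weeks 2, 4, 6 and 8", with the reference to screening gone. Neither section names any other time point for hsCRP.

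Protocol 9.1.3 lists hsCRP among the chemistry tests ("glucose, AST, ALT, GGT, AP, lactate dehydrogenase and hsCRP") and sets the sampling times: "Blood for safety laboratory assessments will be collected at screening, baseline, Weeks 2, 4, 6 and 8". SAP 4.1.2 adds a general rule: "The baseline will be defined as the last available (non-missing) value before or on the day of the first administration of study drug". SAP 4.3 lists hsCRP among the baseline laboratory parameters, but nothing links that to this endpoint.

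SAP 4.6.2 analyses the endpoint with Newcombe intervals at each visit and a logistic model containing treatment, baseline ferritin, baseline TSAT and site, in both the FAS and the PPS.

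**The concern.** The ferritin bar differs about sevenfold between the branches, so the hsCRP value used to classify a subject can decide success or failure. With that value undated, the choice falls to whoever programs the endpoint, in an open-label trial.

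If the hsCRP at each visit were used, the bar would become a post-randomisation quantity. A subject could change from success to failure, or back, because hsCRP crossed its normal limit. The comparison at a visit would then partly reflect movement in hsCRP, and the Week 2 to Week 8 course of this endpoint would mix two definitions within the same subject.

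**Working it through.** **1. Plan figures that depend on the rule.** There are none. The sample size concerns the primary endpoint and serves here only for denominators. With 70% response in both arms, margin 15 points, one-sided 2.5% and 80% power: n = 2 × 0.70 × 0.30 × (1.95996 + 0.84162)² / 0.15² = 0.42 × 7.849 / 0.0225 = 146.5, so 147 per group; 147 / 0.80 = 183.75, so 184 randomised per group. Both agree with SAP 2.4.

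**2. Time point of hsCRP, side by side.**

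| Place | Normal branch | Raised branch |
|---|---|---|
| Protocol synopsis and 11.7.2 | screening | not stated |
| SAP 2.6.2 and 4.6.2 | not stated | not stated |
| Inclusion criterion 3 (Protocol 5.2) | screening | screening |

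The protocol's two branches separate subjects cleanly only if both use screening. If the raised branch used the visit value, a subject normal at screening and raised at the visit would fall in both branches, and one raised at screening and normal at the visit would fall in neither.

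**3. What the choice changes (hypothetical subjects, Week 6, TSAT 20%).**

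| Subject | Screening | Week 6 | Screening hsCRP used | Visit hsCRP used |
|---|---|---|---|---|
| A | hsCRP normal, ferritin 10 | hsCRP raised, ferritin 60 | bar >14: success | bar ≥100: failure |
| B | hsCRP raised, ferritin 60 | hsCRP normal, ferritin 60 | bar ≥100: failure | bar >14: success |

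Subject B is eligible under criterion 3 and meets the lowered ferritin bar with the entry value, so that part of the endpoint needs no iron effect. TSAT must still rise, because entry requires TSAT below 16%. Under the Day 1 reading, both results depend on the Day 1 hsCRP.

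**4. Size within an arm (assumed inputs).** Let s be the share of an arm with normal hsCRP at screening and raised hsCRP at the visit. Let g be the share of those with TSAT of at least 16% and ferritin above 14 but below 100. The correction rate falls by s × g.

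| s | g | Fall (points) | Subjects of 147 | Subjects of 184 |
|---|---|---|---|---|
| 5% | 20% | 1.0 | 1.5 | 1.8 |
| 10% | 50% | 5.0 | 7.4 | 9.2 |
| 20% | 80% | 16.0 | 23.5 | 29.4 |

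Movement from raised to normal raises the rate by the same formula, so the net effect is smaller if both occur.

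**5. Between arms (same assumptions, upward movement only).** The FCM − IS difference shifts by s(IS) × g(IS) − s(FCM) × g(FCM).

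- Equal s in both arms, g differing: 0.05 × (0.50 − 0.20) = 1.5 points up to 0.20 × (0.80 − 0.20) = 12 points, against the arm with the larger g.
- More switching on IS (10% v 5%), g = 50% in both: 5.0 − 2.5 = 2.5 points in favour of FCM.
- The same switching, g = 20% on IS and 80% on FCM: 2.0 − 4.0 = 2.0 points against FCM.

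So the sign is not fixed even if one arm switches more often.

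**The case against.** A reader might infer that the SAP prescribes classification by the hsCRP at each visit. It does not. The hsCRP condition sits inside a closed bracket, and the list of weeks outside it times the TSAT and ferritin assessment. The bracket describes a type of subject, which suggests a fixed attribute. SAP 1 says the SAP is to be read together with the protocol, and Appendix 1 keeps screening when it restates inclusion criterion 3. Screening is therefore the most plausible intention. That limits the point to an unstated time point, but the analysis definition still does not state it. If visit hsCRP were wanted, it would be a departure from the protocol needing a reason.

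A reader might also infer a bias in favour of FCM, because Protocol 2 says that a single administration "reduces the risks associated with the administration procedure, such as phlebitis, infection" compared with multiple infusions. That passage gives no rates and does not mention hsCRP. The direction also depends on how many subjects in each arm have ferritin between the bars, which the documents do not report. The inference is not supported.

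The impact is limited. This is one of five secondary efficacy endpoints, tested without multiplicity adjustment, and the protocol cautions against reading much into any single significant result. Changes in TSAT and ferritin are analysed separately without an hsCRP rule, so the course of iron stores stays readable.

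On the covariate, a randomised comparison does not require an inflammation term, and baseline ferritin partly tracks the stratum. It tracks it only partly: screening ferritin above 14 implies an inflamed entrant, but 14 or below can belong to either stratum. A pre-randomisation factor that sets the outcome threshold is a reasonable model term.

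**Conclusion.** The point holds as a gap in the SAP that should be closed. Both SAP definitions omit a time point that the protocol states for the normal branch, and the protocol itself leaves the raised branch undated. Three readings are open: screening, Day 1 and current visit. That the words are missing is certain; that visit hsCRP would be used is only possible.

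Under the visit reading, an arm's correction rate could fall by 1 to 16 percentage points for s of 5% to 20% and g of 20% to 80%, partly or wholly offset by movement the other way. These inputs are assumptions, not figures from the documents. No between-arm bias has been shown, and its size and direction are unknown. The primary endpoint, its margin and the sample size are untouched.

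**What to change.** - In SAP 2.6.2 and 4.6.2, state that the screening hsCRP used for inclusion criterion 3 fixes each subject's ferritin bar, in both branches, for every visit. Make the same addition to the raised-hsCRP branch in the protocol.
- State how a subject without a screening hsCRP is handled. SAP 4.1.8 allows no imputation here. Appendix 1 makes the missing value a major deviation, which removes the subject from the PPS but not from the FAS.
- Add the screening inflammation stratum as a covariate in the logistic model for iron-deficiency correction.
- As a clerical tidy-up only, write hsCRP where SAP 2.3 and Appendix 1 write CRP.

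The cost is wording, one derived variable and one more model term. Screening hsCRP is already scheduled for every subject, so no new data are needed.
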